## **6.3 Therapeutic Procedures**

### **6.3.1 Avelumab Administration**

Each cycle of Avelumab is 14 days. Avelumab is administered on an outpatient basis. Avelumab 10mg/kg body weight, diluted with 0.45% or 0.9% saline solution, will be administered as a 60 minute intravenous (IV) infusion every 2 weeks, on day 1 of each cycle. No Avelumab dose reductions are permitted on this study. Specific instructions for the preparation infusion fluid and administration of infusion solution are provided in the Pharmacy Manual.

After the initial cycle, the patient will receive 5 additional cycles of adjuvant Avelumab per protocol for a total of 6 cycles. Patients will be evaluated for adverse events/toxicities after receiving the first dose of Avelumab.

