#### 12.4 Stereotactic Body Radiation Treatment

It is reasonable to extrapolate expected toxicity rates from the current experience and reported literature with SBRT. One significant toxicity is radiation pneumonitis, which can be manifested as fever, increased exertional dyspnea, pleuritic chest pain, and peritumoral infiltrate on chest imaging. It generally occurs between 1 to 3 months of completion of radiotherapy. The risk of grade 2-4 radiation pneumonitis is approximately 10-20% in patients treated with conventional large field radiotherapy and higher in patients treated with combined chemoradiotherapy. It is highly dependent on the volume of the lung treated to high dose and the mean lung dose.

Importantly SBRT has a significantly better tolerated with a limited side effect profile compared to conventional large field radiation. For example the rates of Radiation

Pneumonitis with SBRT have been reported as less than 5%. At this point, the incidence of RT pneumonitis from SBRT combined with immunotherapy for small pulmonary tumors is unknown. However, if the proposed radiation dose constraints are used the risk should be <10% with the proposed dose level.

Other toxicities commonly associated with such treatment includes colitis, diarrhea, hypophysitis, rash, arthritis, fatigue, nausea, vomiting, anorexia, and weight loss. Some of these symptoms could also be due to tumor progression. Clinical and radiographic assessments will be performed as indicated to identify all adverse effects, ascertain their etiology, and provide the most appropriate palliative measures. Complications will be graded according to the Common Toxicity Criteria, National Cancer Institute, version 4.0.

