### 4. Identifiable reporting source

The report must contain information that clearly identifies the reporter, which establishes that there was firsthand knowledge of the identifiable subject.

It is important that information regarding an SAE be reported within the established timelines as described in the ‘Required Reporting Times Frames’ section above. If a report is delayed, then the reason for the delay should be clearly explained.

- Examples of reasons for delay:

- ξ Information missed due to clerical issues at the site
- ξ Correction of previously transmitted information

Serious adverse events, or a follow up to a serious adverse event, including death due to any cause other than progression of the cancer under study that occurs to any subject from the time study treatment initiation through 90 days following cessation of treatment, or the initiation of new anti-cancer therapy, requires expedited reporting as described below:

- A) The Study Chair and Site Principal Investigator must be notified within 24 hours of learning of any serious adverse events (SAEs).
- B) The Institutional Review Board (IRB) of each site must be notified by the site principal investigator according to their local policies.
- C) The UCSD Human Research Protections Program (HRPP) and Moores Cancer Center Data and Safety Monitoring Board (DSMB) must be notified within 10 business days of “any unanticipated problems involving risk to subjects or others” (UPR). The following events meet the definition of UPR:
  1. Any serious event (injuries, side effects, deaths or other problems), which in the opinion of the Principal Investigator was unanticipated, involved risk to subjects or others, and was possibly related to the research procedures.
  2. Any serious accidental or unintentional change to the IRB-approved protocol that alters the level of risk.
  3. Any deviation from the protocol taken without prior IRB review to eliminate apparent immediate hazard to a research subject.
  4. Any new information (e.g., publication, safety monitoring report, updated sponsor safety report), interim result or other finding that indicates an unexpected change to the risk/benefit ratio for the research.
  5. Any breach in confidentiality that may involve risk to the subject or others.
  6. Any complaint of a subject that indicates an unanticipated risk or that cannot be resolved by the Principal Investigator.

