## **15. STATISTICAL CONSIDERATIONS**

### **15.1 Endpoints**

#### **15.1.1 Primary Objectives**

Phase I: The Phase I primary endpoint is safety and tolerability as described in Section 3.1.1. Tolerability and safety of will be determined after all patients have completed six doses or have discontinued dosing prior to completing six doses. Safety analyses will be performed in all treated subjects. Descriptive statistics of safety will be presented using National Cancer Institute (NCI) Common Terminology Criteria for Adverse Events (CTCAE) version 4.0.

Phase II: The Phase II primary endpoint is to determine the relapse free survival rate at a median followup of 2 years in early stage NSCLC treated with definitive SBRT combined with 6 cycles of concurrent and adjuvant Avelumab.

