#### **15.2 Sample Size/Accrual Rate**

Phase I: The purpose of the Phase I part of this study is to evaluate the tolerability and safety profile SBRT combined with concurrent and adjuvant Avelumab at 10mg/kg. For this purpose, 12 subjects will be enrolled. Although the sample sizes are not based on statistical power considerations, data from these subjects will provide toxicity and dosing information on administration Avelumab in combination with SBRT in patients with early Stage NSCLC. The accrual rate is estimated at 3 patients per month.

Phase II: The primary endpoint will be relapse free survival (RFS) rate at median followup of 2 years. The accrual rate is estimated at 3 patients per month, and the patients will be

followed for up to 3 years. A total of 56 patients will be entered in the study accounting for a 10% dropout rate. This study would have 80% power to detect a 10% absolute improvement in RFS at 2 years from 80% to 90% using a one-sided t-test at significance level 0.10. RFS estimate at 2 years was based upon analysis of relevant literature[55-57].

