### 15.3 Safety Run-In Phase

There is no significant published experience with SBRT used concurrently with Avelumab in this study population. Therefore, to ensure that the combination is safe, the first six patients will be treated and observed for toxicity for 30 days after radiation before continuing with further treatment. 6 patients will be enrolled at the proposed dose of Avelumab and SBRT. If  $\leq 3$  patients among the safety cohort have a defined toxicity event within 30 days of therapy, we proceed with additional accrual with this regimen to complete a total of 12 patients. If  $\geq 4$  patients among the safety cohort have defined toxicity events we will suspend the study and have the study reviewed by IRB and DSMB committees for further recommendations.

*Toxicity Event:*  $\geq$  grade 3 adverse event (CTCAE v 4.0) with an attribution of possible, probable, or definite.

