### 15.4 Analysis of Primary Objectives

Phase I: If no more than one-third of the subjects permanently discontinue study medication prior to completing six doses due to treatment related adverse events then this combination will be deemed as tolerable and return to the IRB, DMC, and Sponsor for further evaluation and approval prior to proceeding to the Phase II cohort.

If  $\geq 4$  patients in the Phase I cohort permanently discontinue study medication prior to completing six doses due to treatment related adverse events then we will suspend the study and return the study to the IRB and DSMB committees for further evaluation and recommendations.

Phase II: The primary efficacy analysis will be the relapse free survival (RFS) rate in patients with early Stage NSCLC receiving SBRT combined with concurrent and adjuvant Avelumab compared to SBRT alone historical controls. The analysis population includes all registered subjects who have received SBRT and at least 2 cycles of Avelumab.

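### The Phase I tolerability count in Section 15.4 cannot include any treatment-related event that starts after dose 6, which with on-time dosing leaves about 48-63% of the protocol's own pneumonitis window outside it

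*Combined protocol and SAP*

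**What the plan says.** Section 15.2 sets the Phase I size: "For this purpose, 12 subjects will be enrolled". Section 15.1.1 says when the judgement is made: "Tolerability and safety of will be determined after all patients have completed six doses or have discontinued dosing prior to completing six doses".

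Section 15.4 gives the criterion. The combination is tolerable "If no more than one-third of the subjects permanently discontinue study medication prior to completing six doses due to treatment related adverse events", and the study then returns to the IRB, DMC and sponsor for approval before Phase II. The companion sentence suspends the study when four or more "patients in the Phase I cohort permanently discontinue study medication prior to completing six doses due to treatment related adverse events". Both sentences use the same event.

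Section 12.4 says of radiation pneumonitis: "It generally occurs between 1 to 3 months of completion of radiotherapy". It adds that the incidence with SBRT plus immunotherapy is unknown, but should be below 10% if the dose constraints are used.

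The only other numerical Phase I rule is the run-in in Section 15.3, where "the first six patients will be treated and observed for toxicity for 30 days after radiation". It counts related events of Grade 3 or higher. Section 12.5.2 requires expedited SAE reporting "from the time study treatment initiation through 90 days following cessation of treatment", and the Section 10 calendar has an AE evaluation 3 months after SBRT.

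**The concern.** Phase I exists to judge the safety and tolerability of the combination, and pneumonitis is the toxicity that the protocol singles out as uncertain. The rule counts early stopping of avelumab. Once a patient has had dose 6, nothing that happens later can be counted. If all 12 patients received six doses and each then had related Grade 3-5 pneumonitis, the count would be 0 of 12 and the criterion would be met. Longer follow-up does not help, because the limit is in the event definition. At stake is a prespecified finding of tolerability that reviewers would have to override by judgement, with no stated threshold for late events.

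**Working it through.** **The plan's own figure.** Section 6.5 gives a therapy duration of about 3 months. Six 14-day cycles are 84 days, and 84 / 30.4375 = 2.76 months, which agrees.

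**When the count closes.** Avelumab is given "every 2 weeks, on day 1 of each cycle" (Section 6.3.1), so with dose 1 on day 1, dose 6 is on day 1 + 5 × 14 = 71. SBRT starts 3-10 days after dose 1 (Section 6.3.2), on day 4-11. Four or five fractions every other day (Section 6.5) add 6 or 8 days, so SBRT ends on day 10-19. Dose 6 is therefore 71 − 19 = 52 to 71 − 10 = 61 days after SBRT.

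**Share of the window outside the count.** Taking 1-3 months as 30-90 days:
- On time: (90 − 61)/60 = 0.48 to (90 − 52)/60 = 0.63.
- One 14-day delay (dose 6 at 66-75 days): 0.25 to 0.40.
- Two delays (80-89 days): 0.02 to 0.17.

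On-time dosing gives 0.50-0.65 with calendar months and 0.41-0.57 with 28-day months.

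**Does the run-in cover it?** It concerns six patients. Observation for 30 days after radiation ends as the window opens. The threshold sentence in Section 15.3, however, speaks of 30 days from therapy. If that means the last avelumab dose, the run-in reaches 52 + 30 = 82 to 61 + 30 = 91 days after SBRT. Section 15.3 can also be read as pausing avelumab during the observation period. Dose 6 would then fall about 30 + 4 × 14 = 86 days after SBRT, which conflicts with two-weekly dosing. Either reading helps only those six patients.

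**Illustration.** The protocol gives no operating characteristics for this rule. Assume onset uniform over days 30-90, every event before dose 6 leading to discontinuation, no other discontinuations, and a pass at 3 or fewer of 12. The visible share v is (61 − 30)/60 = 0.52 to (52 − 30)/60 = 0.37. Then P(pass) = BinomCDF(3; 12, p × v) for the current rule, against BinomCDF(3; 12, p) if the whole window counted.

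| True rate p | Current rule | Whole window |
|---|---|---|
| 10% | 0.997-0.999 | 0.974 |
| 20% | 0.97-0.99 | 0.80 (0.795) |
| 1/3 | 0.86-0.95 | 0.39 |
| 40% | 0.78-0.91 | 0.23 |

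**Sensitivity.**
- Pass at 4 or fewer, p = 40%: 0.92-0.98 against 0.44.
- Assumed 10% independent early discontinuation from other causes, p = 1/3: the counted probability is 1 − 0.9 × (1 − v/3) = 0.21-0.255, against 1 − 0.9 × 2/3 = 0.40. P(pass) is 0.63-0.77 against 0.23.
- One 14-day delay in every patient, p = 1/3: v = 0.60-0.75, and P(pass) is 0.65-0.79 against 0.39.

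**The case against.** The strongest reply is that this count does not open Phase II. A tolerable result only sends the study to the IRB, DMC and sponsor. Under Section 13 the DMC reviews all available safety data, may meet ad hoc and can recommend termination. Section 15.1.1 also provides descriptive safety analyses in all treated subjects. A discontinuation-based count alongside descriptive safety and committee approval is a recognisable design. This stands. A reader might infer that late severe or fatal pneumonitis would go unseen, or that Phase II would open automatically. The documents support neither. What is missing is a criterion for late toxicity, not data collection or review.

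Second, rates of one-third and above are far from what the protocol expects. Section 12.4 gives under 5% for SBRT alone, below 10% here, and 10-20% (Grade 2-4) for conventional large-field radiotherapy. At 10% the two ways of counting barely differ. This also stands, although Section 12.4 calls the combination rate unknown, and a stopping rule is needed for the case where the expectation is wrong.

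Third, the rule counts discontinuation for any related event, and doses may be delayed. Both narrow the gap, as shown, but do not close it on the 30-90 day window.

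Fourth, a reader might infer that no numerical rule could ever count a late event. Given the loose run-in wording, that is too firm. For six patients the answer depends on how Section 15.3 is read.

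**Conclusion.** The point holds as a fault in the Section 15.4 event definition. That finding needs only the rule's text and the dosing schedule. The share of the pneumonitis window outside the count, 48-63%, rests on on-time dosing and 30-day months; one delay reduces it to 25-40% and two to 2-17%. The pass probabilities rest on uniform onset and on assumed true rates, and illustrate scale only. They show a negligible effect at the expected rate and a large one if the true rate is several times higher. The consequence is a misleading prespecified label passed to the reviewing bodies, not an unguarded route into Phase II. It should be corrected, since the adverse event data are already scheduled.

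**What to change.** 1. In both Phase I sentences of Section 15.4, count a patient as an event if (a) a treatment-related adverse event causes permanent discontinuation before six doses, or (b) a Toxicity Event as already defined in Section 15.3 (Grade 3 or higher, at least possibly related) starts after dose 6 and by the 3-month post-SBRT visit in the Section 10 calendar. The Section 15.3 definition is preferable to asking whether avelumab would have been stopped. That question is hypothetical, and Section 8 is not uniform: Section 8.1 generally discontinues for Grade 3 reactions, while Table 2 allows delay and resumption for Grade 3-4 rash.
2. Amend the timing sentence in Section 15.1.1 so that the determination is made once every Phase I patient has reached that visit or died.
3. Reconcile the two Section 15.4 sentences. With 12 patients one-third is 4, so exactly 4 events is both tolerable and a suspension.
4. Reconcile the two descriptions of the run-in observation period in Section 15.3, and its wording on continuing treatment with the two-weekly schedule.

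Section 8 and all dosing and management rules stay unchanged, and no visit is added. The cost is time: the 3-month visit falls 90 − 61 = 29 to 90 − 52 = 38 days after an on-time dose 6. With the calendar's 4-day visit allowance, the decision comes about 4 to 6 weeks after the last patient's dose 6, and may overlap the planned review. The regimen also becomes slightly less likely to be declared tolerable. At a true rate of 10%, counting the whole window in the illustration gives 0.974 rather than 0.997-0.999.

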#### 6.7 Criteria for Removal of Subjects from Study Treatment and Study

- Unacceptable adverse events grade IV or greater with an attribution of possibly related while on CBI or after SBRT.
  - Subject withdraws consent for follow-up;
  - Subject is lost to follow-up;
  - Subject dies;
  - Study is terminated for any reason.
- ξ The patient has a confirmed positive serum pregnancy test;

ξ General or specific changes in the patient's condition render the patient unacceptable for further treatment in the judgment of the investigator;

ξ Administrative Decision

Subject can elect to discontinue treatment at any time. If participants withdraw from the study, they will be followed for survival data.

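### The Phase I suspension count is set for 12 patients, but patients who leave early for reasons other than related toxicity are neither replaced nor excluded, so the rule loses sensitivity

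*Combined protocol and SAP*

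**What the plan says.** **Phase I rule.** Section 15.2 fixes the cohort: "For this purpose, 12 subjects will be enrolled". It adds "Although the sample sizes are not based on statistical power considerations", and no target toxicity rate or probability of suspension is given. Section 15.4 declares the combination tolerable "If no more than one-third of the subjects permanently discontinue study medication prior to completing six doses due to treatment related adverse events". It suspends the study if four or more "patients in the Phase I cohort permanently discontinue study medication prior to completing six doses due to treatment related adverse events". Only discontinuations for related adverse events enter the numerator.

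**Timing and denominator.** Section 15.1.1 states: "Tolerability and safety of will be determined after all patients have completed six doses or have discontinued dosing prior to completing six doses". The reason for discontinuing does not matter there, and safety is analysed in all treated patients. Section 15.6 makes everyone evaluable for toxicity from the first avelumab dose, with no minimum exposure. Section 11.2 differs: its Safety Population requires avelumab combined with SBRT.

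**Run-in rule.** In Section 15.3 accrual continues to 12 if three or fewer of the first six "among the safety cohort have a defined toxicity event within 30 days of therapy", and the study is suspended at four or more. The event is an at least possibly related adverse event of grade 3 or higher, not a discontinuation.

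**Other ways to leave.** Section 6.7 lists, among others, "Subject withdraws consent for follow-up", loss to follow-up, death, a change in condition and an administrative decision. Patients who withdraw are then followed for survival.

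**Dropout.** The only figure is for the whole study: "A total of 56 patients will be entered in the study accounting for a 10% dropout rate" (Section 15.2). No section gives a replacement rule for Phase I or the run-in.

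**The concern.** A trigger of four has a given sensitivity only if 12 patients (or six in the run-in) can contribute an event. A Phase I patient who withdraws after one dose for a personal reason can no longer become a related-toxicity discontinuation, yet stays among the 12 on the same footing as a patient who completed six doses. Such a patient can never add to the count, so the effect runs one way: suspension becomes less likely.

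Section 15.3 says there is no significant published experience with this combination in this population, and the Phase I rule is the main quantitative check before the 44 Phase II patients.

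**Working it through.** **1. The plan's own figures.** No probability of suspension is stated, so there is none to reproduce. The limits are 4/12 = 33.3% in Phase I and 4/6 = 66.7% in the run-in. Exactly 4 of 12 is one-third, so it satisfies the tolerability sentence and also triggers suspension.

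**2. Phase I, by number of leavers.** Let p be the true rate of related discontinuation and m the number of leavers treated as wholly uninformative and counted as event-free. Then

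P(suspend) = P(X ≥ 4), X ~ Binomial(12 − m, p).

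At p = 0.40 and m = 0: 1 − (0.002 + 0.017 + 0.064 + 0.142) = 0.775.

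| True rate p | m = 0 (12 assessed) | m = 1 (11) | m = 2 (10) |
|---|---|---|---|
| 25% | 35.1% | 28.7% | 22.4% |
| 1/3 | 60.7% | 52.7% | 44.1% |
| 40% | 77.5% | 70.4% | 61.8% |
| 50% | 92.7% | 88.7% | 82.8% |

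The smallest step is 92.7 − 88.7 = 4.0 points and the largest about 9 (52.7 to 44.1).

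**3. Averaged over an assumed early-loss rate d.** If each patient leaves unassessed with probability d, independently of toxicity, the effective rate is p(1 − d). At p = 0.40:

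- d = 1%: rate 0.396, P(X ≥ 4 of 12) = 76.6%, a drop of about 1 point.
- d = 10%: rate 0.360, P(X ≥ 4 of 12) = 68.0%, a drop of about 10 points (77.5 − 68.0 = 9.5).

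The 10% in Section 15.2 belongs to the 56-patient calculation for relapse-free survival at 2 years, not to about 3 months of treatment, so it serves here only as the top of the range.

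**4. Is the one-third limit breached?** A pass means at most three events. With one, two or three leavers this is at most 3/11 = 27%, 3/10 = 30% or 3/9 = 33.3% of the remaining patients, so the limit is respected. Passing above one-third needs at least four leavers (3/8 = 37.5%). Even at d = 10% the chance of four or more leavers in 12 is 2.6%.

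**5. Run-in.** Here m counts only patients whose observation ends inside the window without an event. P(suspend) = P(X ≥ 4), X ~ Binomial(6 − m, p):

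| True event rate | 6 observed | 5 observed |
|---|---|---|
| 1/3 | 10.0% | 4.5% |
| 40% | 17.9% | 8.7% |
| 50% | 34.4% | 18.8% |
| 2/3 | 68.0% | 46.1% |

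With one patient lost, suspension needs 4 of 5 (80%) instead of 4 of 6.

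**6. Size of the tie at 4 of 12.** At a true rate of 1/3, suspending at four or more fires 60.7% of the time; suspending only above one-third (five or more) fires 36.8%. That gap of 23.9 points exceeds the loss from two leavers (60.7 − 44.1 = 16.6).

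**The case against.** The strongest reply is that counting all treated patients is a legitimate convention, that no sensitivity was promised, and that the size depends on an unknown number of leavers. Much of this stands.

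- **Limit.** A reader might infer that leavers let a regimen above the one-third limit pass. Step 4 shows otherwise for up to three leavers: 4 of 11 or 4 of 10 are results at which the rule does suspend.
- **Dropout.** A reader might apply the 10% dropout directly to the first three months. The documents do not support that. If early loss is nearer 1%, the average effect is about 1 point.
- **Run-in.** A reader might infer that anyone who stops avelumab drops out of the run-in count. The event there is a related grade 3 or higher adverse event; visits continue from SBRT completion (Sections 6.4 and 10), and serious events are collected for 90 days after treatment stops (Section 12.5.2). Only lost observation dilutes the count, for example loss to follow-up or a withdrawal after which only survival is tracked.
- **Retention.** Keeping every leaver is what Sections 15.1.1 and 15.6 imply. The Safety Population in Section 11.2 would drop a patient who left before SBRT, so the denominator is unsettled.
- **Oversight.** A Phase I pass goes to the IRB, DMC and sponsor for approval, and the DMC sees all safety data at least every 6 months (Section 13). This mitigates the risk but does not define the count.
- **Bias of replacement.** Replacing every event-free leaver would discard, for instance, someone with five uneventful doses, and would push the observed rate up. This limits the form of the fix.

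**Conclusion.** The point holds as a loss of sensitivity in the Phase I rule. Each of the first two early leavers costs about 4 to 9 percentage points of the chance of suspension at true rates of 25% to 50%, relative to 12 fully assessed patients. With an assumed early loss of 1% to 10%, the average drop at a 40% rate is about 1 to 10 points.

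These are upper bounds, because leavers were at risk for part of the course, and they assume that leaving is unrelated to toxicity. In the run-in the loss is confined to patients whose 30-day observation is incomplete without an event: one such patient in six lowers 34.4% to 18.8% at a true rate of 50%.

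A breach of the one-third limit is not supported. A change is still worth making: the direction is always towards continuing, the denominator differs between sections, and the remedy is cheap.

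**What to change.** - **Section 15.3:** replace a run-in patient whose 30-day observation is incomplete and who had no toxicity event.
- **Section 15.4:** define a minimum exposure at which a patient is evaluable for tolerability, and replace patients who leave below it for a reason other than a related adverse event. Patients at or above it stay in the count.
- **Both rules:** always count anyone who met the event definition, whatever their exposure.
- **Numbers:** take replacements from the 44 Phase II places, so the total stays at 56. Keep replaced patients in the safety listings, and in the relapse-free survival analysis where they meet its population rule in Section 15.4 (SBRT and at least two avelumab cycles).
- **Denominator:** reconcile Sections 11.2, 15.1.1, 15.4 and 15.6 on one denominator, and reconcile the two sentences of Section 15.4 that give opposite readings of exactly 4 of 12.

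The cost is protocol wording. The downside is that the Phase I read may be delayed by the accrual and dosing time of one or two patients, at the planned 3 patients per month and about 3 months of treatment.

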investigated in phase I/II trials. The safety and tolerability of avelumab in a phase I dose escalation trials has been reported (NCT01943461). Additionally the safety and clinical activity in patients with advanced NSCLC progressing after platinum-based chemotherapy has been reported (NCT01772004). In this study (NCT01772004) a prespecified analysis of 184 patients with  $\geq 3$  months follow-up (range 3-13) was performed. Patients were treated with avelumab at 10 mg/kg Q2W until progression, confirmed complete response (CR), or toxicity. Tumors were assessed every 6 weeks (w) (RECIST 1.1) and unconfirmed best overall response (BOR) was evaluated. Median age was 65y (range 31-83) and ECOG PS was 0 (30%) or 1 (70%). Histology was adenocarcinoma (62%), squamous cell carcinoma (29%), or other (9%). Any grade drug-related treatment-emergent adverse events (TEAEs) occurred in 139 (75.5%) pts; the most common ( $> 5\%$ ) were fatigue, nausea, infusion-related reactions (IRRs), chills, decreased appetite, and diarrhea. Drug-related grade  $\geq 3$  TEAEs occurred in 22 (12%) pts, including 4 IRRs. Drug-related deaths were reported (n = 3; radiation pneumonitis, acute respiratory failure, and disease progression). Objective responses (OR) were observed in 22 (12%) pts (95% CI: 7.6, 17.5; 1 CR, 21 partial responses; 18 were ongoing at data cutoff). BOR of stable disease was observed in 70 pts (38%). Median progression-free survival (PFS) was 11.6 w (95% CI: 8.4, 12.1) and the PFS rate at 24 w was 25.4% (95% CI: 18.3, 33.2). The conclusion from this report was that in patients with previously treated NSCLC, Avelumab was administered safely with a toxicity profile similar to other anti-PD-1/anti-PD-L1 agents.

Importantly, not all patients respond to single agent or dual agent CBI and the activity of current agents appears to be limited to certain disease types. Thus the next logical step is combining CBI with surgery, chemotherapy or radiation therapy and understanding how to best incorporate immunotherapy into definitive treatment regimens[1, 11]. Here we will study the combination of SBRT with concurrent and adjuvant Avelumab in NSCLC as a definitive treatment modality.

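### At exactly 4 of 12 Phase I discontinuations, Section 15.4 both deems the combination tolerable and suspends the study

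*Combined protocol and SAP*

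**What the plan says.** Section 15.4 of the combined protocol and SAP gives two decision rules for Phase I, in consecutive paragraphs.

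- **Tolerable.** The condition reads: "If no more than one-third of the subjects permanently discontinue study medication prior to completing six doses due to treatment related adverse events". Where it is met, the stated consequence is that "this combination will be deemed as tolerable and return to the IRB, DMC, and Sponsor for further evaluation and approval prior to proceeding", the next stage being Phase II.
- **Suspend.** The trigger is that 4 or more "patients in the Phase I cohort permanently discontinue study medication prior to completing six doses" for that same reason. The stated consequence here is: "then we will suspend the study and return the study to the IRB and DSMB committees for further evaluation and recommendations".

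The cohort size is fixed in Section 15.2: "For this purpose, 12 subjects will be enrolled". The synopsis gives the same number. Section 15.1.1 puts the tolerability assessment at the end of dosing: it "will be determined after all patients have completed six doses or have discontinued dosing prior to completing six doses". The same section bases the safety analyses on all treated subjects.

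Section 15.3 has a separate run-in rule for the first six patients. Accrual continues if 3 or fewer have a toxicity event, and if 4 or more "patients among the safety cohort have defined toxicity events we will suspend the study". That rule counts grade 3 or higher related events within 30 days, not discontinuations.

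**The concern.** The two rules in Section 15.4 look like complements, but one is written as a proportion that includes its boundary and the other as a count. With 12 subjects the boundary of the proportion is a whole number, and it is the same number at which suspension starts.

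Tolerability is part of the Phase I primary endpoint, and this is its only pass/fail rule. At 4 of 12 the plan supports two opposite statements: the combination is tolerable and approval for Phase II is sought, or the study is suspended and advice is sought. The choice would be made after the data were known, which a prespecified threshold is meant to prevent.

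**Working it through.** **Inputs**

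- Phase I size: n = 12 (Section 15.2 and synopsis).
- Tolerable rule: X/n ≤ 1/3, that is 3X ≤ n (Section 15.4).
- Suspension rule: X ≥ 4 (Section 15.4).
- X is the number who permanently stop avelumab before six doses because of treatment-related adverse events. Both rules use this same event.
- True discontinuation rate p: not given in the documents, so assumed from 10% to 40%.

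**Step 1: do the rules overlap?** For n = 12, 3X ≤ 12 gives X ≤ 4. The complement of that is X ≥ 5, not the stated X ≥ 4.

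| Denominator n | Largest X deemed tolerable | Suspend from | Overlap |
|---|---|---|---|
| 9 | 3 | 4 | none |
| 10 | 3 | 4 | none |
| 11 | 3 | 4 | none |
| 12 | 4 | 4 | X = 4 |

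At n = 12, counts 0–3 are only tolerable, counts 5–12 are only suspend, and X = 4 is both. No count is left without a rule.

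**Step 2: how likely is X = 4?** With 12 independent patients, P(X = 4) = C(12,4) p⁴(1 − p)⁸ and C(12,4) = 495. For example, at p = 0.25: 495 × 0.25⁴ × 0.75⁸ = 495 × 0.003906 × 0.1001 = 0.194.

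| Assumed p | P(X ≥ 4) | P(X ≥ 5) | P(X = 4) |
|---|---|---|---|
| 10% | 0.026 | 0.004 | 0.021 |
| 15% | 0.092 | 0.024 | 0.068 |
| 20% | 0.205 | 0.073 | 0.133 |
| 25% | 0.351 | 0.158 | 0.194 |
| 30% | 0.507 | 0.276 | 0.231 |
| 33.3% | 0.607 | 0.368 | 0.238 |
| 40% | 0.775 | 0.562 | 0.213 |

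The second and third columns are the chances of suspension under cut-offs of 4 and 5.

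**Step 3: is there an anchor in the documents?** The nearest figure is in Section 4.2, for avelumab alone in advanced NSCLC: drug-related grade 3 or higher "TEAEs occurred in 22 (12%) pts, including 4 IRRs". At p = 0.12, P(X = 4) = 495 × 0.12⁴ × 0.88⁸ = 0.037. This is not a discontinuation rate and does not include SBRT, so it is only a reference point.

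**Step 4: does any other text break the tie?** Section 15.3 concerns a different event and only the first six patients. Section 15.1.1 sets the timing of the assessment and the analysis set, not precedence. Neither resolves the case X = 4.

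**The case against.** The strongest reply is that the slip has little practical effect. Both branches hold the study before Phase II and send it to committees, and Section 13 has the DMC reviewing all safety data and recommending whether to continue, modify or terminate. Phase I safety is summarised descriptively and its size is not power-based, so no error rate hangs on the label. This is right, and it limits the consequence. It does not make the two outcomes the same: one is a positive primary conclusion with a request for approval, the other a suspension with a request for advice.

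The suspension rule can also be read as a running stop that acts at the fourth discontinuation, before the end-of-dosing assessment. On that reading the pause comes first and the committees advise. The end-of-phase criterion would still be met at 4 of 12, so the label remains open.

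The trigger is narrow: exactly 4 events with exactly 12 in the denominator. If one enrolled subject is never treated or replaced, the conflict disappears. But 12 is the planned number, so the rule should work at 12.

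Finally, the probabilities rest on assumed rates, and the higher ones need a true rate near one-third. They also ignore that the run-in might already have suspended a very toxic regimen. Both points stand as limits on the size, not on the contradiction.

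**Conclusion.** The contradiction is real and follows from the text and 12/3 = 4 alone; it needs no assumption beyond all 12 planned subjects being counted. It affects one outcome of the Phase I primary decision, and it is most likely to arise when the true rate is close to the one-third limit, where a clear rule is most needed. Its probability depends on an assumed discontinuation rate and on independence between patients. It exposes no patient to unreviewed treatment and does not touch the Phase II relapse-free survival analysis. It should be fixed, but it does not undermine the design.

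**What to change.** Before the Phase I data are reviewed, amend Section 15.4 so that both rules are stated as counts: tolerable if 3 or fewer of the Phase I patients permanently discontinue for treatment-related adverse events before six doses; suspend if 4 or more do. This keeps the suspension count already written and takes the more cautious reading at 4 of 12. It also gives the same result as the one-third criterion when 9 to 11 are treated. With 8 or fewer treated, a limit of 3 would be looser than one-third (3/8 = 37.5%). That is not the planned size, but a clause can cover it if the sponsor thinks it possible.

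The consistent alternative is tolerable at 4 or fewer and suspend at 5 or more. Either is a defensible design; the plan needs to choose one.

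The amendment is one sentence, with no change to sample size, visits or data. Compared with a cut-off of 5, the recommended rule raises the chance of suspension by P(X = 4): about 2 percentage points at a true rate of 10% (2.6% against 0.4%), 7 at 15% (9.2% against 2.4%) and 19 at 25% (35.1% against 15.8%).
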